5.4 COVARIATES

All the covariates have been collected on the paper CRF designed for this study as specified in the study protocol.

Variable	Role	Operational definition
ECOG	Epidemiological datum (covariate)	Risk groups
Patient age at time of diagnosis	Epidemiological datum (covariate)	Age
TNM tumour stage (T describes the size of the tumour and the spread of the cancer to nearby tissue; N (nodes) describes the spread of cancer to nearby lymph nodes and M stands for metastases)	Epidemiological datum (covariate)	Tumour staging
Tumour histology	Epidemiological datum (covariate)	Pathological Anatomy
Fuhrman tumour grade	Epidemiological datum (covariate)	Pathological Anatomy
KPS	Epidemiological datum (covariate)	Risk groups
Previous nephrectomy	Epidemiological datum (covariate)	Surgery
Cardiac, renal, endocrine, autoimmune and hepatic comorbidities.	Epidemiological datum (covariate)	Disease data
Classification of the prognostic risk group	Epidemiological datum (covariate)	Risk groups
Patient baseline status	Epidemiological datum (covariate)	Risk groups
Time elapsed from the nephrectomy to the start of systemic treatment	Epidemiological datum (covariate)	Risk groups
Haemoglobin	Epidemiological datum (covariate)	Risk groups
Corrected calcium	Epidemiological datum (covariate)	Risk groups
LDH levels	Epidemiological datum (covariate)	Risk groups
Lymphocytes	Epidemiological datum (covariate)	Risk groups
Platelets	Epidemiological datum (covariate)	Risk groups
Baseline Neutrophil/Lymphocyte rate and at 6 weeks of treatment, 3 months, 6 months, 9 months, 12 months and then every 6 months.	Epidemiological datum (covariate)	Risk groups

PFIZER CONFIDENTIAL

Variable	Role	Operational definition
Number of metastases	Disease data (covariate)	Disease data
Number of organs with metastases	Disease data (covariate)	Disease data
Time on treatment before reaching CR	Secondary objective	Disease data
Duration of CR	Secondary objective	Disease data
Reason why CR ends: progression, tumour stabilisation or intolerable toxicity	Disease data (covariate)	Disease data
Dosage and regimens of Sunitinib	Treatment data (covariate)/Secondary objective	Treatment data
Temporary treatment interruptions	Treatment data (covariate)	Treatment data
Definitive interruption of treatment after reaching CR	Treatment data (covariate)	Treatment data
Active patient participation in the decision to interrupt the treatment definitively once CR is obtained	Patient empowerment (covariate)/Secondary objective	

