Time on treatment with Sunitinib once CR is reached	Treatment data (covariate)	Treatment data
Local treatment techniques of residual lesions	Secondary objective	Treatment data
PA (pathological anatomy) of the metastasectomy: histology and degree of necrosis	Disease data (covariate)	Disease data
Highest grade of adverse events related to the treatment with Sunitinib	Secondary objective	Treatment data
Serious adverse events (SAEs) during treatment with Sunitinib	Secondary objective	Treatment data
Pharmacological group of second-line treatment after disease progression after a period of time in CR (TKI, mTOR, Immunotherapy)	Secondary objective	Treatment data
Causes of death	Disease data (covariate)	Disease data

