7.2.4. Efficacy analysis

Depending on the **primary objective of the study**, the complete responses (CR) observed in Spanish daily clinical practice in patients with advanced carcinoma with a renal cell component that have received first-line treatment with Sunitinib will be described. All demographic and clinical characteristics will be summarised descriptively.

More specifically, the following baseline features of both patient and tumour will be described:

- Demographic characteristics (age at the start of treatment of the metastatic disease).
- Comorbidities: presence of cardiovascular, hepatic, renal, autoimmune, chronic dermatological, obesity and/or intestinal disease.
- Tumour data: number and site of metastases, tumour histology, Fuhrman grade and presence of tumour necrosis.
- Previous nephrectomy in the treatment of metastatic renal cancer and time elapsed from nephrectomy to the start of systemic treatment.
- Classification of the risk group according to Motzer and/or Heng criteria.
- Patient's baseline status, including ECOG grade, presence of anaemia, corrected calcium, LDH levels, neutrophil and platelet levels.

Central tendency measures (mean and median) and dispersion measures (standard deviation and interquartile range) will be used for the quantitative variables. Frequency distributions (absolute and relative) will be presented for categorical data. Bivariate comparisons between baseline characteristics and events of interest of a continuous nature will be made by parametric tests (Student's t test, one-way ANOVA) or their non-parametric equivalents (Mann-Whitney, Kruskal-Wallis) depending on the distribution of the variables. In the case of categorical variables, the Chi-squared test or Fisher's exact

PFIZER CONFIDENTIAL

test, as applicable, will be used for the comparison of frequency distribution.

The **secondary outcome measures** pertaining to the follow-up time until the event of interest (complete disease remission, disease progression, change of treatment due to unacceptable toxicity or death from any cause) will be described by estimating survival functions using the Kaplan-Meier method. Specific estimates and 95% confidence intervals will be provided for the median, 25th percentile and 75th percentile of the distributions of each secondary variable. The secondary outcome variables related to follow-up time are:

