- Time on treatment with Sunitinib until complete remission of lesions, calculated as the difference between treatment start date and CR confirmation date (2nd CT scan).
- Duration of complete remission (DOR)
- Progression-free survival (PFS) or time from remission to disease progression, change of treatment due to unacceptable toxicity or death. It will be calculated as the time elapsed from the RC confirmation date (2nd CT scan) until the date of progression/death or change of treatment for unacceptable toxicity, as applicable, or else it will be censored on the date of the last patient follow-up.

Taking into account the asymmetry normally observed in the distribution of survival times and that follow-up periods may be uneven (different study entry date), the Kaplan-Meier method will be used to estimate the median time to CR together with its 95% confidence interval. The median will indicate when complete remission of the disease occurred in 50% of patients.

In order to find associations between time to CR and the baseline features of both patient and tumour, a log-rank test will be used for comparison between groups and the determination of the statistical significance of the correlation between each of the baseline variables and the time to complete remission of disease. The following baseline characteristics are considered:

[figure not shown]
- Demographic characteristics
- Comorbidities
- Tumour data
- Prior nephrectomy in the treatment of metastatic renal cancer
- Classification of the risk group according to Motzer and/or Heng criteria.
- Patient's baseline status, including ECOG grade, presence of anaemia, corrected calcium, LDH levels, neutrophil and platelet levels.

This analysis will establish which baseline characteristics are associated with a shorter complete response time to treatment.

As part of the secondary objectives, the doses and treatment regimens observed in the sample will also be descriptively summarised by means of absolute and relative frequencies. In the case of changes in the treatment dose, the frequency of patients with dose increase, dose reduction and changes in the rest regimen will be specified. Similarly, the most frequent reasons for changes in dosage and/or treatment regimen to RC will be reported.

Frequencies of the type of treatment received will be presented, depending on whether it

Pfizer Confidential

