is monotherapy or combination with a local treatment for one or several residual lesions. In the group of patients who received local treatment, the frequency distribution of the techniques used (traditional surgery, radiotherapy and SBRT) will be presented, at the time they are applied, as well as histology, degree of tumour necrosis and the surgical complications reported.

In the sub-sample of patients who discontinue systemic treatment after a period of treatment with maintenance of CR, the most frequent reasons for the decision and the frequency of cases in which the patient was consulted in the decision to discontinue treatment will be reported, and the cases in which it was at the patient's or the investigator's request.

The distribution of frequencies of the pharmacological group by mechanism of action used in patients in the second-line treatment after disease progression will be reported.

Once the descriptive statistics have been presented, and provided that the proportional *hazards* assumption or relative risk of the covariates of interest (patient and tumour baseline conditions, dose and treatment regimen and type of treatment received) are fulfilled, a multivariate Cox regression will be performed to investigate the effect of all prognostic factors on CR/PFS. The *hazards ratio* (HR) will be estimated, along with their 95% confidence intervals, as parameters of association between each one of the predictive factors of response and the time to complete remission or disease progression.

This information will make it possible to produce recommendations for the therapeutic strategy to be followed in patients who obtain complete remission of the macroscopic lesions to the treatment with Sunitinib.

For the safety analysis of treatment with Sunitinib, the percentage of patients who have presented serious and non-serious adverse events explicitly attributed to Sunitinib during treatment will be presented by means of descriptive tables. The frequency of adverse events recorded will be reported based on severity, the highest grade and whether it or they led to a dose interruption or modification.

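### The Cox model in SAP 7.2.4 has no coded covariate list or parameter cap; at an assumed 17-18 parameters in about 90 patients, each coefficient carries about a 9-10% false-positive rate instead of 5%.

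*SAP*

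**What the plan says.** SAP 7.2.4 plans that, if proportional hazards hold, "a multivariate Cox regression will be performed to investigate the effect of all prognostic factors on CR/PFS". Hazard ratios with 95% confidence intervals are to be reported for time to remission and for progression. Three covariate classes are named: "patient and tumour baseline conditions, dose and treatment regimen and type of treatment received". The section then adds: "This information will make it possible to produce recommendations for the therapeutic strategy to be followed in patients".

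No coding, selection rule, shrinkage method or parameter limit is tied to this model. Three other places could be read as supplying the list:

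- The baseline features earlier in 7.2.4 include the risk group (Motzer and/or Heng), "time elapsed from nephrectomy to the start of systemic treatment", and "Patient's baseline status, including ECOG grade, presence of anaemia, corrected calcium, LDH levels, neutrophil and platelet levels".
- The table in SAP 5.4 labels as covariates items known only after CR, such as "Reason why CR ends: progression, tumour stabilisation or intolerable toxicity" and "Time on treatment with Sunitinib once CR is reached", as well as causes of death.
- SAP 7.2.2 gives display categories for descriptive tables.

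SAP 3.2 sets significance at p<0.05. SAP 3.1 states no hypothesis. SAP 4.1 expects close to 90 cases, and SAP 6 imputes no missing values except dates.

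**The concern.** A Cox model with many parameters for its sample size gives standard errors that are too small. Chance associations then pass p<0.05 too often, and confidence intervals cover too rarely. Since nothing limits the parameters, the size of the problem depends on coding decisions taken after the data are seen.

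Two structural faults add to this:

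- **Overlap.** The risk group would be entered beside the variables that define it, so neither set of coefficients has a clear meaning.
- **Timing.** Treatment type would be a covariate for time to CR. Under SAP 4.1.1, local treatment follows sunitinib for lesions that did not respond, so it is settled after that clock starts and partly reflects the course being modelled.

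At stake is whether chance findings, reported with intervals that are too narrow, enter the recommendations that the registry is meant to produce.

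**Working it through.** **Plan's own figure.** There is no sample-size, event or power calculation to reproduce. The nominal figure is p<0.05 (taken as two-sided). As a calibration, null one-covariate Cox models with n=90 rejected in 4.1-6.3% of runs across 12 settings, consistent with 5%.

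**Parameter count (assumed: one per item in 7.2.4).** Age 1, comorbidity 1, previous nephrectomy 1, risk group 1, patient status 6 (ECOG, anaemia, calcium, LDH, neutrophils, platelets), tumour 5 (number and site of metastases, histology, grade, necrosis), dose/regimen 1, treatment type 1. The total is 17, or 18 with time from nephrectomy. This is a low count: the categories in 7.2.2 would give about 45.

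**Events.**

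- Time to CR: every included patient has CR, so about 90 events; 90/17 = 5.3 and 90/18 = 5.0 per parameter.
- PFS: the count is not stated. Assume exponential times and follow-up uniform to F months. Then events = 90 x [1 - (1 - exp(-LF))/(LF)], with L = ln2/median.

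| Median from CR (SAP 2) | F=60 | F=84 | F=120 | F=150 |
|---|---|---|---|---|
| 27.6 months (Czech registry; not called a median there) | 43.5 | 52.5 | 61.6 | 66.7 |
| 7.9 months (single-hospital series, drug alone) | 73.0 | 77.8 | 81.5 | 83.2 |
| 8.2 months (same series, with local treatment) | 72.4 | 77.3 | 81.1 | 82.9 |

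So PFS has 44-67 or 72-83 events, depending on the source. Events per parameter run from 44/18 = 2.4 to 83/17 = 4.9.

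**Null simulation** (n=90, independent covariates, half normal and half binary at 35%, Wald test at 5%, 2,000 datasets per cell). Entries are false positives per coefficient / chance of at least one.

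| Events | 17 parameters | 18 | 5 | 4 |
|---|---|---|---|---|
| 90 | 9.6% / 76% | 9.9% / 79% | 6.2% / 26% | 6.1% / 21% |
| 67 | 9.3% / 75% | 9.8% / 79% | 6.6% / 28% | 5.6% / 20% |
| 52 | 9.2% / 73% | 9.6% / 77% | 5.9% / 25% | 5.7% / 21% |
| 44 | 8.8% / 72% | 9.4% / 76% | 5.8% / 25% | 5.4% / 19% |

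Independent repeats, including correlated covariates and 30-63 events, gave 9.2-10.8% per coefficient at 17-18 parameters. Likelihood-ratio tests gave 9.6-10.6%. The chance of at least one false factor was about 72-81% over all runs. The event count hardly matters.

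**Why the rate doubles.** The true standard error over the reported one was 1.18-1.20 with 17-18 parameters and 1.03-1.08 with 4-5. A 1.96 cut-off on a statistic inflated by 1.18-1.20 rejects with probability 2 x [1 - Phi(1.96/1.18)] = 9.7% to 2 x [1 - Phi(1.96/1.20)] = 10.2%. Nominal 95% intervals therefore cover about 90%.

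**Multiplicity share.** At a true 5% with independent tests, 1 - 0.95^17 = 58% and 1 - 0.95^18 = 60%. For 4 and 5 tests the figures are 19% and 23%.

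**Sparse categories.** In the series cited in SAP 2, no nephrectomy is about 4% and non-clear-cell histology about 4-6%. A fit fails when a category contains no event. With prevalences of 4% and 6% and event fraction f, the probability is about 1 - [1 - (1 - 0.04f)^90] x [1 - (1 - 0.06f)^90]. This gives 2.9% at 90 events, 8.1% at 67 and 22.6% at 44. Simulated failures at 90 and 44 events were 3.4% and 21.6% with 17 parameters, 3.0% and 25.4% with 5, and 2.7% and 22.7% with 2. There were none with 17 parameters and no rare category.

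**Overlap.** Protocol 1 defines the scores. The baseline list repeats 5 of the 6 Heng factors and 4 of the 5 Motzer factors, reading ECOG for KPS (SAP Annex I). Only time from diagnosis to treatment is not repeated.

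**The case against.** The strongest reply is that this is an exploratory registry without a hypothesis, that the SAP promises hazard ratios with intervals rather than a decision, and that a proportional-hazards check comes first. Also, most of the listed items are not strategy variables, so a chance association for platelets or grade would not by itself produce a treatment recommendation, and the sentence on recommendations may refer to the whole section. Much of this stands and limits the consequence. It does not cure the intervals, which are too narrow whether or not p-values are shown. The proportional-hazards check does not limit the number of parameters. Dose/regimen and treatment type, which are strategy variables, are in the same model.

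A reader might infer more than the documents support:

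- *That the 72-81% is all due to overfitting.* Most of it, 58-60%, is what 17-18 independent tests at a true 5% would give.
- *That too many parameters make the fits fail.* The rare categories do that; a cap alone would not prevent it.
- *That PFS will have only 44-67 events.* The same introduction gives 7.9 and 8.2 months from CR to relapse, which imply 72-83 under the same formula. Those medians may cover relapsing patients only, so neither range is established.
- *That the log-rank tests should lose their significance statements.* They serve the association objective listed as primary in Protocol 7.1, and Protocol 8.7 requires an amendment for major changes to the primary analysis.

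**Conclusion.** The concern holds in this form: the model is not pre-specified, and at a lenient coding its coefficients have about twice the nominal false-positive rate (about 9-10%), with standard errors about 1.2 times too small. This rests on one parameter per listed item, no true effects, complete covariates and about 90 patients. Finer coding is worse: 40 parameters gave about 18-29% per coefficient, depending on events. Missing covariates are also worse: with an assumed 60-70 complete cases, 17-18 parameters gave 11-14%. If some factors have real effects, fewer coefficients can be false positives, so the chance of at least one falls.

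The overlap of the risk group with its components and the use of treatment type for time to CR are faults that need no simulation. Sparse categories are a separate problem, with failed fits in about 3-4% of datasets at 90 events and about a quarter at 44. The change should be made, but its weight is moderate because the study is exploratory.

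**What to change.** In SAP 7.2.4, replace the reference to every prognostic factor with a coded list fixed before the data are analysed, on these rules:

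- Enter one named risk score, without its components.
- Leave treatment type out of the time-to-CR model. Keep it for PFS, whose clock starts at CR confirmation, when it is known.
- Exclude the post-baseline items that SAP 5.4 labels as covariates.
- Merge or omit sparse categories.
- Cap the parameters at events among complete cases divided by 10, rounded down, with a fixed drop order that covers every term.

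One possible list is risk group (favourable versus the rest), age, metastatic organs (1 versus 2 or more), initial regimen (two categories, a coding choice only), and, for PFS only, treatment type. The sponsor may choose another list if it is fixed in advance. With all 90 patients complete, this gives 90/4 = 22.5 events per parameter for time to CR. For PFS it gives 67/5 = 13.4, and at 44 events the cap leaves 4 parameters (44/4 = 11).

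Report hazard ratios with 95% intervals as exploratory. State that about a 19-28% chance of at least one false factor per model remains, of which 19-23% is nominal for 4-5 tests. Keep the log-rank tests as planned, labelled exploratory and unadjusted for multiplicity.

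The cost is SAP wording, with no new data. The sponsor should record whether narrowing the Cox model counts as a major change under Protocol 8.7. The statistical cost is that fewer factors are adjusted for together, so residual confounding, for example by grade or comorbidity, is possible.
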